Effectiveness of a Smoking Cessation Algorithm Integrated into HIV Primary Care

Study Protocol

NCT Number: NCT03670316

Date: September 10, 2025

Purpose and Background

Aim 1: Compare the efficacy of Algorithm Treatment (AT) to Enhanced Treatment as Usual (eTAU) control group for smoking cessation among PLWH smokers engaged in HIV clinical care. We hypothesize that the AT group will have a significantly higher proportion of abstinence (biochemically confirmed primary outcome), 24-hour quit attempts, and greater reduction in mean number of cigarettes smoked per day at 6-months post randomization compared to those in the eTAU group.

Aim 2: Characterize provider-, staff-, patient-, and clinic-level facilitators and barriers to integration of AT treatment and examine intervention cost effectiveness in care. We hypothesize that, compared to the eTAU, written pharmacological prescriptions for smoking cessation and provider knowledge and confidence to treat nicotine dependence will be significantly greater in the AT group. We will also describe clinic characteristics such as size, staffing patterns (e.g., number and type of staff, providers, etc.), average number of annual visits by patients, amount of Ryan White funding, and average appointment time to help inform a future wide-scale implementation project across all CNICS sites.

Aim 3: Estimate the cost effectiveness of the intervention relative to the primary smoking outcomes. This will be done by examining the incremental cost per quit of AT vs. eTAU at 3- and 6-months post intervention.

Site and Staff

The University of Alabama at Birmingham (UAB)

[name], Psy.D., Principal Investigator

[name], Co-Investigator

[name], Program Director
[name], Study Coordinator

The University of Washington (UW)

[name] Co-Investigator
[name], Study Coordinator

The Fenway Institute

[name], Co-Investigator
[name], Project Manager
[name], Study Coordinator

Eligibility Criteria & Approach

Eligibility:

CNICS PRO platform will indicate if the patient is eligible or not for the Algorithm study based on smoking scores.

Inclusion criteria:

1. Age 18 or older
2. Receiving HIV care at UAB, UW or Fenway
3. Smoking 5 or more cigarettes per day for the past month. Black and Milds and other cigars don’t count.

Exclusion criteria:

1. Cognitive impairment such that unable to provide informed consent.
2. Non-English speaking

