Carbon Monoxide Test

RA conducts test with participant immediately following consent. If the provider is waiting to see the participant, the CO test can be done after the visit. RA will instruct participant on how to use CO monitor and will step outside of the room while the participant blows into the monitor. Document the results in the tracking log.

Randomization

Randomization will be programmed into the CNICS PRO platform and will occur after the patient consents to the study. The randomization scheme is a 50/50 ratio between the intervention and control arms. Intervention vs. control status will be tracked in the PRO platform.

Intervention Arm:

Provider Confirmation

1. If the patient is in the intervention arm then:
 - a. The patient’s provider will be sent a note in the EMR or give a hard copy note describing which medication the algorithm recommends he/she prescribe the patient.
 - b. RC will send the physician the pharmacotherapy medication sheet (see Appendix) in the EMR for him/her to review the medication option derived from the algorithm, give him/her a hard copy of the pharmacotherapy medication sheet.

Both Arms:

Questionnaire Completion

Give patient additional questionnaires to complete on tablet in separate research room either before or after the visit with provider, depending on the clinic flow that day. If the participant can’t stay to complete the additional questionnaires, you can schedule a time for him to return to complete them, so long as he picks up his prescription at the pharmacy if the provider decides to prescribe him medication. This must be done on the same day as the baseline visit.

Questionnaires:

1. Demographics
2. Smoking Behavior/History
3. Hughes/Hatsukami Withdrawal Scale (HHWS)
4. Fagerstrom Test for Nicotine Addiction (FTND)
5. Questionnaire of Smoking Urges (QSU)
6. Thoughts about Abstinence (TAA)

Texting

Participants will be sent a text-message based survey each week (11 total) between the Initial Visit and the End of Treatment Visit (12 weeks post-Initial Visit). Response options will be listed after every question and participants will respond to the question with the letter or number included in parentheses. The questions below will be administered every week unless otherwise specified.

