2. Patient given QQs (FTND, QSU, HHWS, TAA, Treatment Satisfaction Survey) and QQ on smoking behavior/medication use. -can be done via text/e-mail if unable to come to clinic. Done after patient has seen providers.
3. Give patient \$40 and schedule next study visit.

6 Month Post-Treatment Follow-up:

1. If visit is in person, conduct CO test and document results in tracking log.
2. Patient given QQs (FTND, QSU, HHWS, TAA) and QQ on smoking behavior/medication use. -can be done via text/e-mail if unable to come to clinic. Done after patient has seen providers.
3. Give patient \$50.

Retention Procedures

Continue to attempt to reach the participant up to six months after the final follow-up visit. After the 6-month mark, the participant can be marked lost to follow-up.

Summary of Compensation

Timepoint	Compensation
Baseline	\$20
12 Week End of Treatment	\$40
1 mo Post-Treatment	\$40
3 mo Post-Treatment	\$40
6 mo Post-Treatment	\$50

Data Collection and Management

All study documentation will be kept in locked file cabinets in study personnel's offices at UAB, UW, and Fenway. The CNICS database can only be accessed by CNICS personnel using UAB, UW, and Fenway computers or encrypted laptops.

Data Analysis

Using Pearson's chi-square test for 2 independent proportions, we will analyze the difference in the proportion of participants with 7-day point-prevalence cessation at 6 months between the treatment arms. Participants for whom we do not have 6-month follow-up data will be assumed to be smoking. We do not anticipate any difference in baseline variables between arms, but if differences do exist, we will utilize a multivariate logistic regression model with cessation as the outcome, treatment group as the primary independent variable, and imbalanced variables which are known to be correlated with cessation as additional independent variables. The same approach will be taken for 24-hour quit attempt – dichotomized yes/no – at 6 months. For cigarette reduction, we will look at the change in number of cigarettes smoked per day at baseline and 6-month follow-up. Either a 2 independent sample *t*-test or the non-parametric Wilcoxon Rank-sum test as appropriate will be used to test for a difference in the change in cigarettes per day between the 2 groups. If necessary, an ordinary least squares regression model with change in cigarettes per day as the outcome adjusting for baseline

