In addition to these primary analyses, we will examine outcomes by sex and racial groups to determine moderator effects. For sensitivity analyses, we will exclude participants without 6-month follow-up data. We will also 1) consider count regressions models that can account for time from enrollment until 6 month visit (such as Poisson regression) if actual timing of planned 6-month follow-up visits differs enough between participants; 2) repeat all analyses using end of treatment and 6-month follow-up outcomes; 3) consider employing models that treat site as a clustering variable (such as Cochran-Mantel-Haenszel [41] and Generalized Estimating Equation); and 4) fit longitudinal models with data from all timepoints. These longitudinal models will examine the interaction between treatment group and time. Exploratory analyses will be conducted stratified by site, cigarettes per day at enrollment, and quit goal.

Protection of Human Subjects

Our team has devised a comprehensive plan for ensuring protection of human subjects throughout the course of the proposed study. We will utilize an English-language consent form with common phrasing that describes that no special privileges or considerations will be conferred because of study participation, and that access to medical care will not be affected by the potential participant's decision to enroll in the study. The procedures listed in the following sections detail procedures that have been approved and utilized during recent years of clinical and behavioral trials at each site for collaborative research that utilizes sensitive information from

participants. Our team will make every effort to protect all participants' confidential and private information in order to minimize possible study-associated risks.

All findings related to this research will be available and provided to study participants in accordance with standard practices. Clinical and measurement data used for research studies will be released only in de-identified fashion.

In addition, all study personnel are required to renew Human Subjects trainings annually, or in accordance with their site regulatory mandates.

Study Algorithm

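### The optional GEE sensitivity analysis clusters on only three sites; in its default form it rejects a true null about 25% of the time, while the CMH test named beside it holds about 5%

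*Combined protocol and SAP*

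**What the plan says.** The primary analysis, in the Data Analysis section, is specified as "Using Pearson's chi-square test for 2 independent proportions", applied to "the proportion of participants with 7-day point-prevalence cessation at 6 months between the treatment arms". For the second outcome, "The same approach will be taken for 24-hour quit attempt – dichotomized yes/no – at 6 months".

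The sensitivity analyses follow in the same section. On site, the team will "consider employing models that treat site as a clustering variable (such as Cochran-Mantel-Haenszel [41] and Generalized Estimating Equation". On visit timing, if it varies enough between participants, they will "consider count regressions models that can account for time from enrollment until 6 month visit (such as Poisson regression". The plan does not give:

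- a variance estimator, reference distribution or small-sample correction for the GEE;
- the outcome to which the count model applies;
- whether time enters the count model as an offset or as a covariate.

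The number of sites is fixed by the inclusion criterion "Receiving HIV care at UAB, UW or Fenway". Target Enrollment lists 250, 200 and 150 patients, 600 in total. Individual patients are randomized after consent: "The randomization scheme is a 50/50 ratio between the intervention and control arms". Stratification by site is not mentioned.

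**The concern.** The sandwich variance used in GEE is estimated from the variation between clusters, and it is reliable only when there are many of them. Here there are three. An analyst who follows the text and accepts common software defaults will get a standard error that is too small and too unstable for a normal reference.

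The two methods named for site also do different things. CMH conditions on site as a stratum, whereas GEE treats the sites as a sample of clusters. The plan offers them as examples of one approach and leaves the choice open. A sensitivity analysis is meant to show whether the primary result is robust, and one that rejects a true null one time in four can lend it false support.

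The count model raises a lesser question. A 7-day abstinence status, or a yes/no quit attempt, does not accrue in proportion to elapsed days. An exposure offset would assume that it does.

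**Working it through.** The plan states no alpha, quit rate or false-positive rate, so there is no figure of its own to reproduce.

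**Inputs from the protocol:** three sites of 250, 200 and 150; individual 1:1 randomization; binary outcomes.

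**Assumptions:** two-sided alpha 0.05; no treatment effect; quit rates of 5–20%, equal or unequal across sites, with one check at 30/40/50%.

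**GEE, by formula.** Take an arm-only logistic model with independence working correlation. The residuals sum to zero within each arm, so the three site contributions to the log odds ratio also sum to zero and carry only 2 degrees of freedom. If the sites were of equal size, the sandwich variance would average (K−1)/K = 2/3 of the true variance, and the z statistic would behave as √(3/2) times a t variable with 2 df. For 2 df, P(|t| > c) = 1 − c/√(2 + c²).

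- Normal reference: c = 1.96 × √(2/3) = 1.600, so the rejection rate is 1 − 1.600/√4.561 = 0.251.
- t(2) reference, critical value 4.303: c = 4.303 × √(2/3) = 3.513, so the rejection rate is 1 − 3.513/√14.342 = 0.072.
- t(2) reference with the variance multiplied by K/(K−1) = 3/2: the factors cancel, leaving 0.05.

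**GEE, by simulation of the null with the planned site sizes:**

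| Method | Rejection at nominal 5% |
|---|---|
| GEE, sandwich, normal reference (closed form, 40,000 trials per scenario) | 24.9–26.2% |
| GEE in software, independence (4,000 trials) | 23.9–26.5% |
| GEE in software, exchangeable (4,000 trials) | 24.8–28.0% |
| GEE in software, either structure (800 trials) | 26.6–29.1% |
| GEE, bias-reduced sandwich, normal reference | 15–16% |
| GEE, t(2) reference | 7.0–7.6% |
| GEE, t(2) and K/(K−1) factor | 4.7–5.3% |
| CMH by site | 4.9–5.2% |
| Logistic regression, site as fixed effect | 4.6–5.3% |

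The formula and the simulations agree on about 25%, and the quit rate makes little difference.

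**Count model, if time is an offset.** With arm as the only covariate, the fitted rate in each arm is events divided by total time. If abstinence is equal in the arms, the rate ratio tends to (mean time, control)/(mean time, intervention). The base time depends on the reading of the 6-month visit. Aim 1 counts from randomization (about 182 days). The Follow-up Visits section counts from the end of 12 weeks of treatment (84 + 182 = 266 days). Suppose that control visits run 45 days later, which is an assumption:

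- 182-day base: 227/182 = 1.25.
- 266-day base: 311/266 = 1.17.

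Simulation with abstinence assumed near 12% gives ratios of about 1.16–1.23 and 7–16% rejection, depending on the base and on whether the standard error is robust. A 14-day delay gives about 4–6%, and equal timing about 3–5%. A larger assumed gap, visits at 8 versus 10 months, gives a ratio near 1.24 and 14–26% rejection with robust errors. With log time as a covariate and a robust variance, rejection is 4.3–5.4% in all the timing scenarios tried (9 v 9, 9 v 10 and 8 v 10 months).

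**The case against.** The best defence is that the plan commits to very little. Both models are ones the team will only consider, and the count model also depends on how visit timing turns out. CMH, which is sound with three strata, is named first in the same sentence. The 25% belongs to a software default, and a suitable small-sample correction brings GEE back to about 5%. All of this stands, and it limits the point to a minor one. It does not remove it, because the plan contains no such correction, and one that leaves 2 degrees of freedom is a poor use of 600 patients when CMH is available.

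A reader might infer four stronger things that the documents do not support:

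- *The plan has a fixed false-positive rate near 28%.* That is towards the upper end of the simulated range, and it presumes a sandwich error with a normal reference, which the plan does not specify.
- *The plan treats abstinence as an accruing count.* It names neither the outcome nor an offset. Aim 1 also lists 24-hour quit attempts, and a number of attempts would be a genuine count, although the Data Analysis section dichotomizes them.
- *Visit timing will create a spurious effect.* Nothing suggests that visits run later in one arm. Both arms share a schedule, and the plan's trigger is variation between participants. Variation alone does not inflate the error rate.
- *Model-based Poisson errors on binary data produce false positives.* They are too large by 1/√(1−p), which makes the test conservative.

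**Conclusion.** The concern holds for GEE clustered on site. In its usual form, with three sites, it rejects a true null about 25% of the time (24–29%), roughly five times nominal, against about 5% for CMH or site fixed effects. This rests on a two-sided alpha of 0.05, the assumed quit rates, and a default sandwich error with a normal reference.

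The count-model point holds only conditionally: a binary outcome, time as an offset, and mean timing that differs by arm. Its size depends on a delay that the documents do not give. What can be said without assumption is that the outcome and the role of time are unspecified.

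The primary Pearson test does not depend on either model. Severity is minor.

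**What to change.** Revise the sensitivity paragraph of the Data Analysis section as follows.

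1. **Site.** Remove GEE clustered on site. State that site will be handled as a stratum by CMH, or as a fixed effect in logistic regression, and choose one before the data are seen. Keep GEE for the longitudinal models, clustered on participant.
2. **Visit timing.** Name the outcome. For 7-day cessation and yes/no quit attempt, use logistic regression, or log-binomial or Poisson regression with robust variance, with visit time as a covariate and no offset. Fit it among participants who have a visit, since those counted as smoking for lack of 6-month data may have no visit time. Note that visit time is measured after randomization, so this analysis is supportive only.

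Treating provider as the cluster instead is not advised: patients are randomized individually and no provider numbers are given. A repeat restricted to in-window visits would need window limits, which the documents do not state.

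The cost is wording only. Sample size, data collection and the primary analysis do not change.
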